9.1.7 Local Skin Reaction (LSR)

Local skin reaction based on known response to PDT (Levulan package insert) will be graded by visual assessment on a custom 4 point scale where 0=none, 1=mild, 2=moderate, 3=severe. Each of the following four reactions will be graded: erythema, vesiculation/postulation, crusting/scabbing/erosion, and edema/swelling. A composite

score will be calculated (range 0-16). LSR assessment will be performed at days 1, 8, 29, and 84.

9.1.8 Symptom assessment

The patient symptom assessment will measure three axes: pain, stinging/burning, and itching/pruritus. Each of these three will be scored by patient report on a numeric scale (0= none, 10= worst possible). Each symptom will be scored and a composite score will be calculated (range 0-30). All subjects will have symptom assessments at 15, 30, 45, 60, and 75 minutes (Table 2). These times allow equivalent assessments relative to medication application regardless of treatment protocol.

A Universal Pain Assessment Tool demonstrating the numeric scale, verbal descriptor scale, and activity tolerance scale will be provided to assist patients in selecting their pain level (Appendix IV).

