8.4.1 Dosage/Dosage Regimen

Aminolevulinic acid HCl topical solution 20% (Levulan Kerastick) will be applied topically once by a healthcare provider on the day of treatment. One Levulan Kerastick will be applied to the treatment area on the face or scalp. Care will be taken to avoid the eyes and mouth.

Treatment arms are as follows:

- A. Conventional arm:** Acetone preparation, ALA topical application, 1 hour incubation, 16:40 BLU-U exposure, application of sunscreen.
- B. Combination arm:** Acetone preparation, ALA topical application, 15 minute incubation, 16:40 BLU-U exposure, application of sunscreen, 45 minute daylight exposure.
- C. Daylight arm:** Acetone preparation, ALA topical application, 15 minute incubation, application of sunscreen, 1 hour daylight exposure.

Due to photosensitivity, subjects should avoid sunlight, tanning beds, and any prolonged or intense light exposure for 40 hours after application of ALA HCl, outside of the assigned treatment regimen. Subjects should not wash or clean their faces until all steps of treatment have been completed.

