9.1.11 Adverse Events

Information regarding occurrence of adverse events will be captured throughout the study. Duration (start and stop dates and times), severity/grade, outcome, treatment and relation to study drug will be recorded on the case report form (CRF).

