10.2 Visit 2 (Day 1, may be combined with Screening)

Unblinded investigator:

1. Randomization to treatment arms (1:1:1). Investigator will use sequential envelopes with randomly prefilled treatment arms. Envelopes will be filled in batches of three (nine patients) to ensure even allocation between arms during the course of treatment.
2. Perform and record vital signs.
3. Concomitant medications and Adverse Events review.

Blinded investigator:

4. Perform abbreviated physical examination.
5. Perform an AK count
6. Perform a pre-treatment local skin response assessment
7. Curette any hypertrophic AK
8. Application of ALA

Unblinded investigator:

9. Monitor ALA incubation duration depending on treatment arm
10. Light exposure (BLU-U and/or sunlight, depending on treatment arm)
11. Symptom assessment. All subjects will have symptom assessments at 15, 30, 45, 60, and 75 minutes (Table 2).
12. Skindex-16
13. Record any Adverse Events.
14. Photography of treatment area.

Blinded investigator:

15. Perform a post-treatment local skin response assessment

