12 DISCONTINUATION AND REPLACEMENT OF SUBJECTS

12.1 Early Discontinuation of Study Drug

A subject may be discontinued from study treatment at any time if the subject or the investigator, or the Sponsor feels that it is not in the subject's best interest to continue. The following is a list of possible reasons for study treatment discontinuation:

Subject withdrawal of consent (or assent)

Subject is not compliant with study procedures

Adverse event that in the opinion of the investigator would be in the best interest of the subject to discontinue study treatment

Protocol violation requiring discontinuation of study treatment

Lost to follow-up

Sponsor request for early termination of study

Positive pregnancy test (females)

If a subject is withdrawn from treatment due to an adverse event, the subject will be followed and treated by the Investigator until the abnormal parameter or symptom has resolved or stabilized.

All subjects who discontinue study treatment should come in for an early discontinuation visit as soon as possible and then should be encouraged to complete all remaining scheduled visits and procedures.

All subjects are free to withdraw from participation at any time, for any reason, specified or unspecified, and without prejudice.

Reasonable attempts will be made by the investigator to provide a reason for subject withdrawals. The reason for the subject's withdrawal from the study will be specified in the subject's source documents Refer to Section 10 for early termination procedures.

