APPENDIX III. TIMING OF SYMPTOM ASSESSMENTS

Min	Symptom Assessment	Conventional Arm	Combination Arm	Daylight Arm
0		Begin 1 hour Incubation	Begin 15 minute incubation	Begin 15 minute incubation
5		Incubation	Incubation	Incubation
10		Incubation	Incubation	Incubation
15	X	Incubation	Sunscreen, BLU-U Exposure: 16m 40s	Sunscreen, Daylight Exposure: 60m
20		Incubation	BLU-U	Daylight
25		Incubation	BLU-U	Daylight
30	X	Incubation	End BLU-U, Begin Daylight Exposure: 60m	Daylight
35		Incubation	Daylight	Daylight
40		Incubation	Daylight	Daylight
45	X	Incubation	Daylight	Daylight
50		Incubation	Daylight	Daylight
55		Incubation	Daylight	Daylight
60	X	BLU-U Exposure: 16m 40s	Daylight	Daylight
65		BLU-U	Daylight	Daylight
70		BLU-U	Daylight	Daylight
75	X	End BLU-U, Sunscreen	End Daylight	End Daylight

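### No symptom score is required when light stops early on Day 1, so in early stoppers the 75-minute score is not pain at the end of exposure: up to 15 minutes late in arm A, up to 60 in arms B and C

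*Combined protocol and SAP*

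**What the plan says.** Section 5.1 makes pain at the end of exposure the second part of the primary endpoint. Section 15.3 compares it between the three arms by unpaired t-tests.

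Section 9.1.8 fixes the Day 1 readings ("All subjects will have symptom assessments at 15, 30, 45, 60, and 75 minutes (Table 2"), and section 10.2, step 11, repeats them. The reason given is comparability from drug application: "These times allow equivalent assessments relative to medication application regardless of treatment protocol".

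The timing table in Appendix III places the end of light in the 75-minute row for all arms; for arm A that cell reads "End BLU-U, Sunscreen". Section 15.3 does not say which reading is the end-of-exposure value.

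Section 12.1 allows early stopping: "A subject may be discontinued from study treatment at any time". It also asks subjects who stop to attend an early discontinuation visit at the earliest opportunity. The procedures for that visit (section 10.8) include a symptom assessment.

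**The concern.** The readings follow the drug clock, whereas the endpoint is defined by the light. The two agree closely when the full light course is given. They separate when light is cut short, because the plan then asks for no reading at light-off. The 75-minute score is still due, so the value is mistimed rather than missing, and nothing in the data set would flag it.

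Arm A is the simplest case. Its only readings in the light window are at minute 60, as light starts, and at minute 75. A subject who stops in between has no scheduled reading under light after it starts. The end-of-exposure score is then taken with the light off, and the peak score may miss the pain that caused the stop.

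A momentary pain score cannot be recovered later, so an analysis plan written after the data are collected cannot repair this.

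**Working it through.** **Inputs.** Readings at 15, 30, 45, 60 and 75 minutes after ALA (9.1.8). Arm definitions from 8.4.1: arm A, 60 minutes of incubation then 16:40 of BLU-U; arm B, "15 minute incubation, 16:40 BLU-U exposure, application of sunscreen, 45 minute daylight exposure"; arm C, 15 minutes of incubation then 60 minutes of daylight. Sunscreen application is taken as instantaneous.

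**Planned end of light, against the plan's 75 minutes.**

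- Arm A: 60:00 + 16:40 = 76:40
- Arm B: 15:00 + 16:40 + 45:00 = 76:40
- Arm C: 15:00 + 60:00 = 75:00

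In completers the 75-minute score is thus 1:40 before light-off in arms A and B, and at light-off in arm C. One Appendix III cell for arm B reads "End BLU-U, Begin Daylight Exposure: 60m", but that table's own timeline ends daylight at 75, which fits 45 minutes.

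**Lag in early stoppers**, if the 75-minute score is used (lag = 75 minus the actual end of light):

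| Case | Light ends | Lag (min) | Largest |
|---|---|---|---|
| A, stop at t, 60 to 75 | t | 75 − t | 15 |
| B, all treatment stopped during BLU-U at s, 15:00 to 31:40 | s | 75 − s | 60 |
| B, stop during daylight at v, 31:40 to 75 | v | 75 − v | 43:20 |
| B, BLU-U cut at s before 30, full daylight at once | s + 45 | 30 − s | 15 |
| C, stop at u, 15 to 75 | u | 75 − u | 60 |

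Examples: an arm A stop at 65 gives 75 − 65 = 10 minutes. In arm B, BLU-U cut at 20 with full daylight gives 30 − 20 = 10. An arm C stop at 60 gives 75 − 60 = 15. If an analyst used the next scheduled reading instead, the lag would be at most 15 minutes in any arm, but no rule says so.

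**Yardstick.** Section 15.6 gives a detectable pain difference of 1.25 points with 10 per arm, two-sided alpha 0.05 and power 0.8, but no SD. The normal formula gives SD = 1.25 / [(1.96 + 0.84) × √(2/10)] = 1.00; the t-test version gives 0.94. Without a stated SD the figure cannot be confirmed. It serves here only as a scale.

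**Size, on assumed values.** Let p be the stop rate in an arm and d the points of pain lost between light-off and minute 75. Neither is in the documents. The expected shift in the arm mean is p × d:

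- p = 2%, d = 1: 0.02 points (0.02/1.25 = 1.6%)
- p = 5%, d = 3: 0.15 points (12%)
- p = 10%, d = 5: 0.50 points (40%)

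One actual stopper moves a 10-subject mean by d/10, which is 0.1 to 0.5 for d from 1 to 5, with a ceiling of 1.0 on a 0 to 10 scale. The chance of no stopper in an arm is (1 − p)^10: 0.82, 0.60 and 0.35 at p = 2%, 5% and 10%.

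**Direction.** The measured A minus C difference shifts by −(p × d in A) + (p × d in C). With 5% × 3 in A and 2% × 1 in C it is −0.15 + 0.02 = −0.13. With those values swapped it is −0.02 + 0.15 = +0.13. The sign depends on where the stops occur.

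**The case against.** - **The fixed clock is deliberate.** It is, and section 9.1.8 says why. That is a good reason to keep the 75-minute score. It does not turn a score taken after light-off into an end-of-exposure score.
- **The plan already has a symptom score triggered by stopping.** A reader might infer from 9.1.8 alone that there is none; sections 12.1 and 10.8 show otherwise. A subject who stops on Day 1 is on site with the coordinator who scores symptoms, so the visit could be held at once. But it is not timed to light-off, and no rule makes its score the endpoint value. This narrows the gap without closing it.
- **Other records cover the stop.** For adverse events, section 9.1.11 says "Duration (start and stop dates and times), severity/grade, outcome, treatment and relation to study drug will be recorded", and section 13 calls for a violation form. These would largely give the time and reason of a symptom-driven stop, but not a 0 to 10 score.
- **LOCF covers it.** The 75-minute score is still taken, so nothing is missing. If it were missed and LOCF applied, an arm A stopper would carry forward the minute-60 score, taken as light starts.
- **It is a contingency.** This stands. No document gives a rate of interrupted light, and section 12.1 is general wording applied to a single treatment session. The trial calls itself small and descriptive.
- **The absence cannot be fully checked.** Appendix II is a figure that could not be read here, and section 15 defers analysis detail to a later SAP. A SAP can choose among collected scores but cannot supply one that was never taken.

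**Conclusion.** The gap is real and minor. For a subject whose light ends early, the 75-minute score is not pain at the end of exposure. The lag reaches 15 minutes in arm A, 60 in arm C, and 60, 43:20 or about 15 in arm B depending on how the stop occurs. Completers are little affected.

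Two stronger readings are tempting. The first is that 15 minutes is the worst case in the trial; that holds for arm A only. The second is that any bias must work against daylight and so could not produce a false claim in its favour. If pain eases after light-off (an assumption), stops in arm A understate arm A pain, but stops in arms B or C understate theirs, after possibly longer lags. The documents do not show where stops would occur, so the net direction is unknown. Nor do they show that any stop will occur, so they do not support calling the endpoint invalid.

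**What to change.** In sections 9.1.8 and 10.2 (step 11) and Appendix III, add:

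> If a subject's light exposure (BLU-U or daylight) ends before its assigned time, the coordinator scores all three symptoms at that moment and records the clock time and reason. If the last light exposure ends before minute 75, the symptoms are also scored at that end. All scheduled scores, including minute 75, are still taken.

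In section 15.3, add:

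> The end-of-exposure value is the score at the actual end of the last light exposure if that is before minute 75, and otherwise the 75-minute score (within 1:40 of the planned light-off). A sensitivity analysis uses the 75-minute score for all subjects. Peak uses the scheduled readings, with a sensitivity analysis that adds the light-off readings.

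The two endpoints are handled differently because peak is a maximum: an extra reading given only to stoppers can only raise it. The end-of-exposure value remains one reading per subject. The main peak analysis may still miss pain at the stop, and its sensitivity analysis shows by how much.

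The cost is protocol and CRF wording, plus one or two three-item scores per stopper, taken by the coordinator who already gives the light and scores symptoms (section 8.2). The downside is a few off-schedule, outcome-triggered readings and some loss of equal timing from drug application in those subjects. The retained 75-minute score and the sensitivity analyses address this.

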9.1.9 Skindex-16

Skindex-16 is used to measure quality of life in patients with skin diseases. The Skindex-16 will be administered on Days 1, 3, 8, 15, 29, 84, and early termination (if applicable).

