15.4 Analysis of Secondary Endpoints

Efficacy and tolerability data will be summarized by each secondary endpoint.

Symptom level over time during the treatment period will be graphed for visualization along the three axes of pain, stinging/burning, and itching/pruritus as well as a composite symptom score. Peak symptom level during the treatment period and pain at the end of treatment exposure will be compared between the conventional treatment arm (A), the combination treatment arm B), and the daylight treatment arm (C), with unpaired t-tests.

Percent reduction in the number of actinic keratoses and proportions of patients with partial and complete clearance of actinic keratoses will be presented descriptively and visualized as histograms. We will compare the percent reduction in the number of AKs and the proportions of patients with clearance between the conventional treatment arm (A) and the combination treatment arm B), and between the conventional treatment arm (A) and the daylight treatment arm (C), using unpaired t-tests.

All analyses will be based on the intent-to-treat (ITT) population. In the ITT population, patients will be counted in the treatment group upon randomization, regardless of receiving any dose of study medication. For efficacy analysis, all missing values due to patient early termination from the study will be imputed using last observation carried forward (LOCF) method, as appropriate. For each patient, the Baseline values will be defined as those values recorded at Day 1 prior to dosing. Patients who are lost-to-follow-up after Baseline will be included to the ITT population carrying forward their Baseline values.

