APPENDIX VI. SKINDEX-16

During the past week, how often have you been bothered by:	Never Bothered ↓	●	Always Bothered ↓
1. Your skin condition itching	 0	 1	 2  3  4  5  6
2. Your skin condition burning or stinging	 0	 1	 2  3  4  5  6
3. Your skin condition hurting	 0	 1	 2  3  4  5  6
4. Your skin condition being irritated	 0	 1	 2  3  4  5  6
5. The persistence / reoccurrence of your skin condition	 0	 1	 2  3  4  5  6
6. Worry about your skin condition (For example: that it will spread, get worse, scar, be unpredictable, etc)	 0	 1	 2  3  4  5  6
7. The appearance of your skin condition	 0	 1	 2  3  4  5  6
8. Frustration about your skin condition	 0	 1	 2  3  4  5  6
9. Embarrassment about your skin condition	 0	 1	 2  3  4  5  6
10. Being annoyed about your skin condition	 0	 1	 2  3  4  5  6

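### The Day 1 Skindex-16 is listed after treatment and none is given at Screening, so no Skindex-16 score meets the plan's own Baseline definition

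*Combined protocol and SAP*

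**What the plan says.** Section 9.1.9 sets the schedule: "The Skindex-16 will be administered on Days 1, 3, 8, 15, 29, 84, and early termination (if applicable"). It does not say when on Day 1. Appendix I gives Skindex-16 one mark on Day 1 and none at Screening, and the Screening list in 10.1 does not include it. For Local Skin Reaction, by contrast, Appendix I shows separate pre- and post-treatment assessments on Day 1.

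The Day 1 order comes from the numbered list in 10.2:

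- Step 1: randomisation by envelope.
- Step 6: "6. Perform a pre-treatment local skin response assessment"
- Step 7: curettage of hypertrophic lesions.
- Step 8: "8. Application of ALA"
- Step 10: "10. Light exposure (BLU-U and/or sunlight, depending on treatment arm")
- Step 11: "11. Symptom assessment. All subjects will have symptom assessments at 15, 30, 45, 60, and 75 minutes (Table 2")
- Step 12: Skindex-16.
- Step 15: "15. Perform a post-treatment local skin response assessment"

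The form in Appendix VI opens with "During the past week, how often have you been bothered by". Section 15.4, repeated in the Synopsis, states that "the Baseline values will be defined as those values recorded at Day 1 prior to dosing".

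**The concern.** A score taken at step 12 is not a pre-dose score. If the list is followed as printed, the study will hold no Skindex-16 value that qualifies as Baseline under 15.4, and the Day 1 form is the only one that precedes follow-up.

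The order matters because of what the form asks. Its first four items concern itching, burning or stinging, hurting and irritation. Just before completing it, the subject has rated pain, stinging/burning and itching five times. The primary objective is to find out whether these sensations differ between arms, and under 8.2 the subject knows the treatment received. If conventional treatment does hurt more, the Day 1 score could be raised most in that arm. A summary of change from Day 1 would then show more quality-of-life improvement in the arm that was harder to tolerate. What is at stake is the interpretation of six scheduled administrations per subject with 10 subjects per arm, not the trial's main result.

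**Working it through.** The plan states no figure for Skindex-16, so there is none to reproduce. The check compares the sections and then does some simple arithmetic.

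**1. Is there a pre-dose score?** ALA is step 8 and Skindex-16 is step 12 (10.2). Screening has no Skindex-16 (10.1, Appendix I). Baseline requires a Day 1 value before dosing (15.4). Number of scheduled Skindex-16 values that qualify: 0.

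**2. Is the list in time order?** It alternates between unblinded and blinded staff and brackets treatment with a pre-treatment skin assessment at step 6 and a post-treatment one at step 15. That supports reading step 12 as after treatment. It remains an inference, because no sentence says so.

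**3. How much of the form overlaps with treatment symptoms?** There are 16 items, each scored 0 to 6 (Appendix VI).

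- Maximum raw total: 16 × 6 = 96.
- Items 1-4: 4 × 6 = 24, which is 24/96 = 25% of the range.

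**4. How would this enter a change score?** Higher scores are worse. Let treatment on Day 1 raise each of items 1-4 by a in the conventional arm and by c in the daylight arm. Change is follow-up minus Day 1, so the conventional-minus-daylight difference in change is shifted by −4(a − c). The documents give no value for a − c. The values below are assumptions.

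| Assumed a − c per item | Shift in raw total (0-96) | Rescaled to 0-100 |
|---|---|---|
| 0.5 | 4 × 0.5 = 2 | 100 × 2/96 = 2.1 |
| 1.0 | 4 × 1.0 = 4 | 100 × 4/96 = 4.2 |

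If a = c, the shift is 0. If a > c, the conventional arm looks more improved than it is.

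**5. How far does past-week recall dilute this?** Appendix III runs the treatment session to 75 minutes. A week has 7 × 24 × 60 = 10,080 minutes, and 75/10,080 is about 0.7% of the recall period. On a literal reading of a frequency question, the effect would be slight. Recent discomfort may weigh more than its share of the week, but the documents offer nothing to measure that.

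**6. What do the later recall weeks cover?** Treatment is on Day 1, and section 10 allows ±3 days for every visit.

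- Day 3, nominal: 3 − 1 = 2 days after treatment, so about 7 − 2 = 5 of the 7 recall days precede it.
- Day 8, nominal: 8 − 1 = 7 days after treatment, so the recall week runs essentially from treatment onward.
- Day 8 held at its earliest, Day 5: 5 − 1 = 4 days after treatment, so about 7 − 4 = 3 recall days precede it.
- Day 15 held at its earliest, Day 12: 12 − 1 = 11 days after treatment, so none do.

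**The case against.** The strongest reply is that no planned analysis is affected. Skindex-16 is not among the primary endpoints (5.1, 15.3) or the secondary endpoints (5.2), and section 15 describes no Skindex-16 comparison, whether of change or otherwise. This stands, and it limits the weight of the point.

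A second reply is that the form covers a week in which treatment takes up little more than an hour, so the Day 1 score may be close to an untreated one. If Day 3 is discounted because most of its recall week precedes treatment, the same reasoning protects Day 1. This also stands, as a reason to expect a small effect. It does not make the score pre-dose.

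A third reply is that the numbering is not a strict clock. The step 11 ratings start during incubation, and 10.1 lists consent again at step 9 although section 9 requires it before any study activity. This stands in part: the timing is probable rather than certain. But if the list does not fix the order, then nothing in the plan does, and the same clarification is needed.

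A reader might go further and infer that Day 1 scores are bound to be contaminated unequally by arm, and that the damage cannot be undone. The documents do not support this. The arm difference in symptoms is the trial's hypothesis, not a known fact. Because the arms are randomised, follow-up Skindex-16 scores can be compared directly without using Day 1. Only a change score, or adjustment for the Day 1 score, would carry the problem.

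A reader might also infer that no pre-treatment photograph exists, since Day 1 photography is step 14. Section 10.1 lists one at Screening.

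**Conclusion.** The point holds as a gap in the Day 1 order for a supporting instrument. On the printed sequence, no Skindex-16 value satisfies the Baseline definition in 15.4. Any summary of change from Day 1 could be biased in favour of the more symptomatic arm, by an unknown and possibly small amount. The range of 2 to 4 raw points out of 96 only illustrates an assumed arm difference of 0.5 to 1 point on each of four items; it is not an estimate.

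The conclusion rests on reading 10.2 as chronological. The direction of any bias rests on the trial's own hypothesis that symptoms differ by arm. The primary and secondary endpoints are untouched, and between-arm comparison of follow-up Skindex-16 scores remains valid without Day 1. The change is worth making because it costs nothing and because a pre-dose score cannot be collected once a subject has been treated.

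**What to change.** - In 10.2, move Skindex-16 ahead of step 1, so that it is completed before the envelope is opened and before curettage and ALA. Placing it just before step 7 would not be enough, because the arm is assigned at step 1 and the coordinator who administers the form is unblinded (8.2).
- State the same timing in 9.1.9 and Appendix I, and name this score as the Skindex-16 Baseline, in line with 15.4.
- In the SAP that section 15 promises, state that Day 3, and any Day 8 visit held early in its window, has a recall week that mixes pre- and post-treatment days, and interpret those scores accordingly.
- If subjects have already been treated under the printed order, compare follow-up scores between arms without using Day 1.
- While editing, reconcile the Screening photograph in 10.1 with 9.1.10 and Appendix I, which do not list it.

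Cost: a reordering of steps and a few sentences. No visit, form or staff time is added.
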